¹ The screening process will generally involve up to 3 visits, and most screening procedures will be performed within these designated visits (S1 S3). However additional screening visits may be needed for some procedures, e.g., MRI ██████████. In addition, it may sometimes be necessary for participants to return for repeat assessments (e.g., if the MRI scan does not pass the quality control process). Brain MRI (S2) will only be performed after the participant has met the eligibility criteria and has acceptable laboratory tests from Visit S1. ██████████

² The clinical assessments performed during Visit S1 are to be administered in the order specified: 1) MMSE; 2) neuropsychological tests in the following order: ISLT, DSST, Trails A, Category Fluency and Letter Fluency tests from the DKEFS, ISLR; 3) CDR. Note that the Visit S1 results from CDR, ISLT/ISLR, and MMSE will be used to determine participant eligibility; Visit S3 ISLT assessments will provide baseline measures. At Visit S3, the clinical assessments will be administered as follows: 1) neuropsychological tests in the following order: ISLT, DSST, Trails A, Category Fluency and Letter Fluency tests from the DKEFS; 2) ADAS-Cog 13; 3) QoL-AD.

³ It is recommended that all the screening procedures be completed within 65 days; however, the overall Screening Period may be extended up to 90 days in consultation with the Medical Monitor in advance and provided that written documentation is received from the Sponsor or delegate (██████████). The following screening assessments should be repeated if the Screening Period is >65 days: confirmation of eligibility criteria, ██████████

CONFIDENTIAL

The information contained herein may not be used, disclosed, or published without the written consent of Biogen MA Inc.

abbreviated medical history, and physical examination. In addition, some cognitive and /or safety assessments may require repeating depending on the duration of the screening window extension, in discussion with the Medical Monitor.

⁴ All assessments and blood collection during dosing days will be performed prior to infusion, unless otherwise specified. Doses should be administered at least 21 days apart.

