- ⁴ Pregnancy testing is required for women of childbearing potential only; for these participants, a serum pregnancy test is to be performed at EOS [or ET] Visits, and a urine pregnancy test is to be performed at every dosing visit.

- [REDACTED]
- ⁶ Triplicate 12-lead (paper) ECGs will be obtained at each specified timepoint. ECGs are to be performed in triplicate, with each ECG performed about 1 minute apart and before blood draws on appropriate days. Each ECG must be performed after the participant has been resting (supine) for 10 minutes. ECGs will be read by a central reading facility. Clinical significance of potential ECG abnormalities will be determined by the Investigator.
 - ⁷ Vital signs will include SBP, DBP, heart rate, body temperature, and respiratory rate and will be measured with the participant supine and after the participant has been resting for at least 10 minutes. In addition, blood pressure and heart rate will be measured after the participant has been standing for ≥ 2 minutes at the following timepoints: preinfusion and 1 hour (± 15 minutes) after the end of infusion on Weeks 80, 84, 88, and 92. Single vital sign readings will be obtained at other timepoints.
 - ⁸ Brain MRI may include, but will not be limited to, the following sequences: 3D T1 weighted, fluid attenuated inversion recovery, T2* weighted, diffusion weighted imaging, and proton density/T2 weighted MRI. For further details on MRI sequences, please see the procedural manual for MRI. During the LTE period, the visit date for the MRI can vary by ± 10 days from the specified visit day.

CONFIDENTIAL

The information contained herein may not be used, disclosed, or published without the written consent of Biogen MA Inc.

[REDACTED]

¹²It is recommended that postbaseline CDR assessments be conducted at the same time of day at which the baseline assessment was performed to avoid diurnal variation. The rater who conducts the CDR for a participant/informant cannot complete any other rating scales for that same participant/partner or be the study site coordinator and will be blinded to all other study-related data.

[REDACTED]

¹⁴Participants' tobacco use status will be assessed while collecting information on concomitant therapies.

CONFIDENTIAL

The information contained herein may not be used, disclosed, or published without the written consent of Biogen MA Inc.

Table 3: Schedule of Activities for Week 132 Through Week 176 of the Long-Term Extension Period

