3.4 Dates and Points of Reference

The study day and baseline are defined for each analyses period respectively

1. LTE period

- Study Day 1: the date of the first dose of study treatment in the LTE period
- Study Day
 - For a date on or after Study Day 1

$$\text{Study Day} = (\text{Date of Interest}) - (\text{Study Day 1}) + 1$$
 - For a date before Study Day 1

$$\text{Study Day} = (\text{Date of Interest}) - (\text{Study Day 1})$$
- LTE baseline: the baseline value for the LTE period is defined as the most recent non-missing measurement collected prior to the first dose in the LTE period.
- Change from baseline will be defined as post-baseline value minus baseline value

2. Placebo-controlled and LTE period

- Study Day 1: the date of the first dose of study treatment in the PC period

CONFIDENTIAL

The information contained herein may not be used, disclosed, or published without the written consent of Biogen MA Inc.

- Study Day
 - For a date on or after Study Day 1
Study Day = (Date of Interest) – (Study Day 1) + 1
 - For a date before Study Day 1
Study Day = (Date of Interest) – (Study Day 1)
- PC and LTE baseline: the baseline value for the Placebo-controlled and LTE period is defined as the most recent non-missing measurement collected prior to the first dose in the PC period.
- Change from baseline will be defined as post-baseline value minus baseline value

3. Placebo-controlled and LTE active treatment period

- Study Day 1: the date of the first dose of BIIB092. For low-dose, medium-dose and early start high-dose subjects, this will be the date of first dose of BIIB092 in the placebo-controlled (PC) period; for late start high-dose subjects, this will be the date of first dose of BIIB092 in the LTE period.
- Study Day
 - For a date on or after Study Day 1
Study Day = (Date of Interest) – (Study Day 1) + 1
 - For a date before Study Day 1
Study Day = (Date of Interest) – (Study Day 1)
- Active treatment baseline: the baseline value for the active treatment period and is defined as the most recent non-missing measurement collected prior to study day 1.
- Change from baseline will be defined as post-baseline value minus baseline value

For data that are summarized by visit, assessment from all scheduled visits, EOS visit and unscheduled visits will be mapped to an appropriate analysis visit using a windowing scheme as describe in [Appendix I](#)

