	Statistical Analysis Plan Long-Term Extension Period	V1.0
---	---	-------------

Potential serious hepatotoxicity

In this SAP, we define potential serious hepatotoxicity as ALT or AST > 3x ULN and total bilirubin > 2x ULN at any time post-baseline in the placebo-controlled and LTE active treatment period (not necessarily concurrent). A scatterplot of the maximum post-baseline ALT or AST value relative to ULN and maximum post-baseline total bilirubin value relative to ULN (not necessarily concurrent) for each subject will be provided. A line plot of ALT, AST, ALP and total bilirubin values over time in the active treatment period for subjects with potential serious hepatotoxicity will be provided. In addition, subjects with ALT > 1x ULN, >3x ULN, >5x ULN, >10x ULN or >20x ULN, subjects with AST > 1x ULN, >3x ULN, >5x ULN, >10x ULN or >20x ULN, subjects with total bilirubin >1x ULN or >2x ULN, subjects with ALP >1x ULN or >1.5x ULN, and subjects with AST or ALT > 3x ULN post-baseline accompanied by concurrently elevated total bilirubin >1.5x ULN or > 2x ULN in the active treatment period will be presented. A listing of subjects with potential serious hepatotoxicity will be provided with the concurrent records labeled. Concurrent is defined as on the same day.

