5.4.5 ECG Data

5.4.5.1 ECG analyses

Actual values of numeric ECG parameters will be summarized by visit. number of evaluable subjects, mean, standard deviation, 25% and 75% quartiles, min and max values will be presented at each visit for placebo-controlled and LTE period active treatment period. Similarly change from baseline values will be summarized in the same fashion for placebo-controlled and LTE active treatment period.

Summary of ECGs (number of normal, <abnormal, not adverse event>, or <abnormal, adverse event>) at scheduled visits will be presented by the LTE treatment group through the placebo-controlled and LTE active treatment period.

CONFIDENTIAL

The information contained herein may not be used, disclosed, or published without the written consent of Biogen MA Inc.

	Statistical Analysis Plan Long-Term Extension Period	V1.0
---	---	-------------

Shift table from normal or unknown ECG at baseline to ever abnormal ((<abnormal, not adverse event>, or <abnormal, adverse event>) post-baseline ECG will be summarized for the placebo-controlled and LTE active treatment group. The worst post-baseline record of each subject is selected.

For the above mentioned ECG analyses, for early start subjects, the placebo-controlled baseline will be used while for late start subjects, the LTE baseline will be used.

In addition, PR and QTcF values will be summarized. Please see the detail in the SAP for placebo-controlled period.

Visit windows for by visit summaries

For ECG data that are summarized by visit, assessment from all scheduled visits, EOT visit, EOS visit and unscheduled visits will be mapped to an appropriate analysis visit using a windowing scheme ([Appendix I](#)).

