5.8 Additional Exploratory Endpoints

5.8.1 Health Outcomes

The FAS will be used for the analysis of health outcomes data for LTE period. The result will be listed by LTE treatment group for placebo-controlled and LTE period.

CONFIDENTIAL

The information contained herein may not be used, disclosed, or published without the written consent of Biogen MA Inc.

6 Appendix I: Visit Window Mapping

For data that are summarized by visit and longitudinal analysis, assessment from all scheduled visits including EOT visit and EOS visit, and all unscheduled visits will be mapped to an appropriate analysis visit using a windowing scheme. Analysis visit windows are defined in [Table 1 - Table 12] for different endpoints.

If there are 2 or more assessments from visits other than EOT or EOS visits mapped to the same analysis visit for a subject, the assessment that is closest to the target visit day will be used for analysis. If there are 2 or more assessments from visits other than EOT or EOS visits mapped to the same analysis visit with the same distance from the target visit day, then select the later one(s) for the analysis. If there are 2 or more assessments from visits other than EOT or EOS visits mapped to the same analysis visit and on the same day, use the average value for quantitative parameters and the worst value for qualitative parameters for analysis.

Table 1. Visit Windows for Efficacy Endpoints

Efficacy Endpoint	Analysis visit	Target visit day	Analysis visit window
CDR, NPI-10, ADAS-Cog13, FAQ, and ADCS-ADL	Baseline	1	Most recent non-missing pre-dose value
	Week 24	169	[2, 267]
	Week 52	365	[268, 456]
	Week 78	547	[457, the end day of the placebo-controlled period ¹]
	Week 104	729	[one day after the start day of the LTE period ² , 813]
	Week 128	897	[814, 981]
	Week 152	1065	[982, 1149]
	Week 176	1233	[1150, 1317]
	Week 200	1401	[1318, 1492]
	Week 226	1582	≥1493
ISLT, DKEFS, DSST, Trails A,	Baseline800-	1	Most recent non-missing pre-dose value
	Week 12	85	[2, 141]
	Week 28	197	[142, 239]
	Week 40	281	[240, 337]
	Week 56	393	[338, 435]
	Week 68	477	[436, 512]
	Week 78	547	[513, the end day of the placebo-controlled period ¹]
	Week 108	757	[one day after the start day of the LTE period ² , 841]

CONFIDENTIAL

The information contained herein may not be used, disclosed, or published without the written consent of Biogen MA Inc.

Efficacy Endpoint	Analysis visit	Target visit day	Analysis visit window
	Week 132	925	[842, 1009]

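### SAP 3.4 ends the active-treatment baseline before the first dosing day, so the liver counts in 5.4.3.2 would take an early-start Day 1 pre-infusion result as post-baseline on BIIB092

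*SAP*

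**What the plan says.** SAP 3.4 defines a baseline for each analysis period. For the combined placebo-controlled and LTE period it is the "most recent non-missing measurement collected prior to the first dose in the PC period", and the LTE baseline is worded the same way around the first LTE dose. For the active treatment period, the baseline is "defined as the most recent non-missing measurement collected prior to study day 1", and the same item sets "Study Day 1: the date of the first dose of BIIB092". For early-start subjects that date falls in the placebo-controlled period, and for late-start subjects in the LTE.

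Protocol Table 1 schedules hematology, chemistry and urinalysis on Study Day 1, and its footnote on dosing days says "All assessments and blood collection during dosing days will be performed prior to infusion, unless otherwise specified".

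SAP 5.4.3.2 opens by stating that the qualitative laboratory analyses take every value, not one record per visit window. Its part on potential serious hepatotoxicity then counts elevations "at any time post-baseline in the placebo-controlled and LTE active treatment period". It also tabulates subjects above successive ULN multiples for ALT, AST, total bilirubin and ALP in the active treatment period. That part does not say which baseline applies.

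**The concern.** Two baselines end at a dose and the third ends at a date. The difference matters only when a value exists on the dosing day before the infusion, and for early-start safety labs the protocol creates such a value.

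The liver counts are absolute multiples of ULN, so the baseline value does not enter them. Baseline matters only as the dividing line that decides which records are post-baseline. If that line falls before Day 1, a sample taken before any BIIB092 was given joins the on-drug records. An early-start subject whose ALT was raised only before the first infusion would then appear in the on-treatment table. Late-start subjects have no matching extra reading. Safety is the primary LTE objective, and the SAP assigns most safety tables to this analysis period, so its dividing line should be unambiguous.

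**Working it through.** **Which records count as baseline**

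- SAP 3.4 numbers the first-dose date as Day 1 and the day before as Day -1. There is no Day 0. A Day 1 pre-infusion sample therefore lies on Study Day 1, not before it.
- Early start, labs: ending at the first dose makes the Day 1 pre-infusion sample the baseline. Ending before Study Day 1 moves the baseline back to Screening Visit 1, nominally up to 65 days earlier (90 if screening is extended), and the Day 1 sample becomes post-baseline.
- Late start, labs: Protocol Table 2 schedules none at Week 80, and the first LTE labs are at Week 100. The last scheduled labs before LTE dosing are at Week 78 (Day 547, against Day 561 for Week 80, 14 days earlier). Both wordings select Week 78.

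**Which outputs depend on the wording**

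- Laboratory change (5.4.3.1), shift and potentially clinically significant abnormalities (5.4.3.2), the general ECG analyses (5.4.5.1) and vital-sign change (5.4.6.1) all name the placebo-controlled baseline for early start and the LTE baseline for late start. Both end at the first dose. These outputs are unaffected.
- The hepatotoxicity and ULN-multiple outputs name neither. They are defined on the active treatment period, which for early-start subjects includes all placebo-controlled and LTE data (3.2). The only baseline that 3.4 attaches to that period is the one ending before Study Day 1. Visit windows do not screen out the Day 1 record, because all values are used.

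**Size**

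The documents give no abnormality rates, so *q*, the chance per visit of a value above 1x ULN without any drug effect, is an assumption. With *K* independent visits, P(ever) = 1 - (1 - q)^K, and one extra reading adds q(1 - q)^K. The placebo-controlled lab visits in SAP Appendix I Table 2 are Weeks 12, 24, 48, 72 and 78, so K = 5. Week 90 applies only to subjects who do not enter the LTE.

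| q | K = 5 | K = 6 (Day 1 added) | relative rise |
|---|---|---|---|
| 1% | 4.9% | 5.9% | 19% |
| 2% | 9.6% | 11.4% | 19% |
| 5% | 1 - 0.95^5 = 22.6% | 1 - 0.95^6 = 26.5% | 17% |
| 10% | 41.0% | 46.9% | 14% |

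At 5% the increment is 0.05 x 0.95^5 = 3.9 points. Two variations reduce it:

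- *LTE visits counted.* With three LTE lab visits added, 1 - 0.95^8 = 33.7% becomes 1 - 0.95^9 = 37.0%, an increment of 3.3 points.
- *Clustering within person.* Let each person's rate follow Beta(0.3, 5.7), with mean 5%, given a normal screening value. The chance of no abnormality in five visits is (6.7/7)(7.7/8)(8.7/9)(9.7/10)(10.7/11) = 0.840. A sixth reading multiplies this by 11.7/12, giving 0.819. P(ever) goes from 16.0% to 18.1%, an increment of 2.1 points.

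Late-start figures do not change under any of these.

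**The case against.** The strongest reply is that the sentence in 3.4 is a stray. The term active treatment baseline is not used again after that section. The endpoint sections and the Appendix I tables use pre-dose or pre-infusion baselines throughout, and Table 9 maps the LTE vital-sign baseline to the Week 80 pre-dose reading. The liver text also sits in a section that has just named the placebo-controlled and LTE baselines twice. A programmer would probably carry those over. This is fair, and it limits the reach of the problem. It does not settle the liver outputs, because those baseline sentences are written for the shift and potentially clinically significant analyses and are not extended to what follows.

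It is also true that 1x ULN is the mildest threshold and that exclusion criterion 21 removes impaired liver function at screening. Unequal follow-up moves the early- versus late-start comparison far more. At 5% per visit with two LTE lab visits, early start is 30.2% (seven visits) and late start 9.8% (two visits) before any Day 1 reading, which takes early start to 33.7%. All of this stands and keeps the point minor.

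Three stronger readings are tempting, and the documents do not support them:

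- *Same-day labs, ECGs and vital signs are generally discarded as baseline.* The sections listed under the check contradict this.
- *PR/QTcF and the vital-sign outliers also fall back on 3.4.* SAP 5.4.5.1 says "In addition, PR and QTcF values will be summarized" and then sends the reader to the placebo-controlled SAP for detail. The outlier criteria in 5.4.6.1 do the same. That SAP is not among the documents, so the baseline these outputs use cannot be asserted.
- *The ECG baseline uses one tracing of the triplicate.* The protocol says "Triplicate 12-lead (paper) ECGs will be obtained at each specified timepoint", but Appendix I Table 6 lists Baseline as an analysis visit. The Appendix I rule for same-day records, "use the average value for quantitative parameters and the worst value for qualitative parameters for analysis", can therefore already cover the baseline triplicate.

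**Conclusion.** Wrong as written, minor severity. SAP 3.4 is internally inconsistent. The consequence that can be traced in these documents is confined to the potential-hepatotoxicity and ULN-multiple counts for early-start subjects, where a pre-drug Day 1 result would be post-baseline.

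Across the assumed range of 1% to 10% per visit, the inflation with five independent visits is about 1 to 6 points for a 1x ULN threshold. These sizes rest on assumed rates, and on independence except in the clustered case. No estimate is available for the combined signal of ALT or AST above 3x ULN with bilirubin above 2x ULN. The AE and SAE analyses, which carry the primary LTE endpoint, do not use this baseline and are unaffected.

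**What to change.** In the active-treatment item of SAP 3.4, end the baseline at the dose and not the date: *prior to the first dose of BIIB092 (including pre-infusion assessments on that day)*. Equivalently, state that it is the placebo-controlled baseline for early-start subjects and the LTE baseline for late-start subjects. In the hepatotoxicity part of 5.4.3.2, add that post-baseline means after that dose.

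The cost is one phrase and one sentence. No new data are needed, and no baseline already named in 5.4.3, 5.4.5 or 5.4.6 changes.

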3.5 Key Derived Variables

- Handling of missing items for scales
 - If any of the individual items for the primary efficacy endpoint and exploratory efficacy endpoints is missing, the total score of the corresponding endpoint will be imputed by prorating the observed scores [van Ginkel 2010].
 - For ADAS-Cog13, if 3 or fewer of 13 items (<25%) are missing, the total score will be imputed by the following algorithm: Total score = total score from the completed items * [maximum total score (=85) / maximum total score for the

CONFIDENTIAL

completed items]. The imputed number will be rounded up to the nearest integer. If more than 3 items are missing, the total score of ADAS-Cog 13 at that visit will be considered missing.

- For ADCS-ADL, if 8 or fewer of 32 items (<25%) are missing, the total score will be imputed by a similar algorithm as that for ADAS-Cog 13. The imputed number will be rounded down to the nearest integer. If more than 8 items are missing, the total score for ADCS-ADL at that visit will be considered missing.
- The same imputation algorithm will be applied to CDR-SB and MMSE, if only 1 box (of 6) of CDR is missing or if only 2 or fewer items (out of 11) are missing for MMSE. The imputed CDR-SB will be rounded up to the nearest half integer, and the imputed MMSE will be rounded down to the nearest integer. If the score from more than 1 box of CDR or more than 2 items of MMSE is not available, the CDR-SB or MMSE at that visit will be considered missing.
- The total score of the tertiary endpoint NPI-10 and FAQ will be imputed using the same prorating principle and round up to the nearest integer if only 1 item (out of 10) is missing.

- iADRS derivation

The iADRS is a composite score based on ADAS-Cog and ADCS-iADL (instrumental ADCS-ADL) [Wessels et al. 2015, Wessels et al. 2018]. The iADRS is calculated as a linear combination of total scores of the two individual components, the ADAS-Cog13 (score range 0 to 85) and the ADCS-iADL (score range 0 to 59). Because higher score on the ADAS-Cog13 reflect worse performance, whereas higher scores on the ADCS-iADL reflect better performance, the ADAS-Cog score is multiplied by (-1) in the calculation of the integrated scale. To anchor the ADAS-Cog at 0, a constant (85) is added. The iADRS score is then computed as the sum of the transformed ADAS-Cog13 and the ADCS-ADL, as shown in the formula below:

$$\text{iADRS score} = [(-1) (\text{ADAS-Cog13}) + 85] + \text{ADCS-iADL}$$

The iADRS score ranges from 0 to 144 with lower scores indicating worse performance. If either ADAS-Cog13 or ADCS-iADL is missing, the iADRS score will be considered missing.

- EMACC derivation

The EMACC is a new and sensitive composite of well-known and validated neuropsychological tests that is suitable for examining the effect of disease modifying compounds on cognitive decline in the early Alzheimer Disease or MCI stage of Alzheimer's disease [Jaeger et al. 2018].

Cognitive variables (ISLT, DKEFS Category Fluency total correct score, DKEFS Letter Fluency, DSST, Trails A total time to complete) will be z-score transformed using the

CONFIDENTIAL

The information contained herein may not be used, disclosed, or published without the written consent of Biogen MA Inc.

baseline score’s mean and SD. The EMACC will be computed by taking the average of the z-scores across the five tests. If Trails A is missing, EMACC will be computed by taking the average of the z-scores across the remaining four tests. For the rest 4 component scores, if any of them is missing then the composite score will be missing.

- ADCOMS derivation

ADCOMS is a novel instrument developed to improve the sensitivity of currently available cognitive and functional measures for subjects in the prodromal stage of AD and mild AD dementia. It consists of 4 Alzheimer’s Disease Assessment Scale–cognitive subscale items, 2 Mini-Mental State Examination items, and all 6 Clinical Dementia Rating—Sum of Boxes items (Table 1). The composite score is a weighted linear combination of the individual scales items using the corresponding partial least squares (PLS) coefficients as weighting factors as listed in Table 1 [Wang et al. 2016]. If any of the individual item is missing, then the composite score will be missing. The range of ADCOMS is between 0 and 1.97.

Table 1. Items included in ADCOMS and their corresponding PLS coefficients

Scale	Item name	PLS coefficients
ADAS-cog	Delayed word recall	0.008
	Orientation	0.017
	Word recognition	0.004
	Word finding difficulty	0.016
MMSE	Orientation time	0.042
	Drawing	0.038
CDR-SB	Personal care	0.054
	Community affairs	0.109
	Home and hobbies	0.089
	Judgement and problem solving	0.069
	Memory	0.059
	Orientation	0.078

ADAS-cog, Alzheimer’s Disease Assessment Scale–cognitive subscale; CDR-SB, Clinical Dementia Rating, sum of boxes; MMSE, Mini-Mental State Exam; PLS, partial least squares.

	Statistical Analysis Plan Long-Term Extension Period	V1.0
---	--	-------------

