Blood sample for BIIB092 concentration				X	X ²⁰	X	X ²⁰	X	X	X ²⁰	X				X ²⁰				X				X ²⁰			X

CONFIDENTIAL

The information contained herein may not be used, disclosed, or published without the written consent of Biogen MA Inc.

Study Week	Baseline Screening Period ^{1, 2} within 65 days ³ of Day 1			Placebo-Controlled Period ⁴																				UV for Change in AD Medication ⁵	FUV ⁶	
	S1	S2	S3 ⁸	1	4	8	12	16	20	24	28	32	36	40	44	48	52	56	60	64	68	72	76 EOT			78/ EOS or ET ⁷
Study Day	S1	S2	S3 ⁸	1	29 ±7	57 ±7	85 ±7	113 ±7	141 ±7	169 ±7	197 ±7	225 ±7	253 ±7	281 ±7	309 ±7	337 ±7	365 ±7	393 ±7	421 ±7	449 ±7	477 ±7	505 ±7	533 ±7	547 ±7		631 ±7
Blood sample for plasma and serum biomarkers ⁴				X				X							X			X					X			
Brain MRI ²²		X									X						X								X ²³	
CDR ²⁸	X									X							X							X	X	
NPI-10			X							X							X							X		
ISLR	X																									
ISLT	X		X				X			X				X				X			X			X	X	
DKEFS Category Fluency and Letter Fluency tests	X		X				X			X				X				X			X			X		
DSST	X		X				X			X				X				X			X			X		

CONFIDENTIAL

The information contained herein may not be used, disclosed, or published without the written consent of Biogen MA Inc.

Study Week	Baseline Screening Period ^{1, 2} within 65 days ³ of Day 1			Placebo-Controlled Period ⁴																				UV for Change in AD Medication ⁵	FUV ⁶		
	S1	S2	S3 ⁸	1	4	8	12	16	20	24	28	32	36	40	44	48	52	56	60	64	68	72	76 EOT			78/ EOS or ET ⁷	
Study Day	S1	S2	S3 ⁸	1	29 ±7	57 ±7	85 ±7	113 ±7	141 ±7	169 ±7	197 ±7	225 ±7	253 ±7	281 ±7	309 ±7	337 ±7	365 ±7	393 ±7	421 ±7	449 ±7	477 ±7	505 ±7	533 ±7	547 ±7		631 ±7	
Trails A	X		X				X				X			X				X			X				X		
eCog (39-item version)			X								X							X							X		
ADAS-Cog 13 ²⁹		X	X							X							X								X	X	
FAQ			X							X							X								X	X	
ADCS-ADL			X							X							X								X	X	
C-SSRS ²⁹		X	X							X							X								X		
MMSE	X						X			X				X			X				X				X	X	
RUD-Lite			X						X							X					X				X if ET		
ZBI			X						X							X					X				X if ET		
QoL-AD			X						X							X					X				X if ET		
AE reporting				Monitor and record continuously beginning on Study Day 1 at the start of dosing																							
SAE reporting				Monitor and record continuously throughout the study																							
Concomitant therapy and procedures reporting				Monitor and record continuously throughout the study																							

CONFIDENTIAL

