5.3.4 Exploratory Efficacy Endpoints

The clinical endpoints assessing AD progression from Baseline include the results of the MMSE, ADAS-Cog13, ADCS-ADL, ISLT, eCog, FAQ, NPI-10, EMACC (composite score of ISLT, DKEFS, DSST, and Trails A), ADCOMS (composite score of selected items from CDR, MMSE, and ADAS-Cog 13) and iADRS.

The by visit summary and MMRM analysis will be performed for MMSE, ISLT, eCog, ADCS-ADL, FAQ, ADAS-Cog-13 (13-item), NPI-10, EMACC, ADCOMS, and iADRS as described in Section 5.3.2.1. For LTE interim analysis at PC DBL, all available records up to week 104 will be analyzed in MMRM table. The baseline and change from baseline scores at each post-baseline visit will be summarized by LTE treatment group at final analysis.

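### SAP Section 3.5 prorates totals with missing items and limits this for six scales, but sets no limit for the 39-item eCog

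*SAP*

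**What the plan says.** SAP Section 3.5 opens its rules on missing scale items with a general sentence. Its trigger is "If any of the individual items for the primary efficacy endpoint and exploratory efficacy endpoints is missing" and its action is that "the total score of the corresponding endpoint will be imputed by prorating the observed scores". That sentence sets no minimum number of answered items.

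Scale-specific conditions follow:

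- "For ADAS-Cog13, if 3 or fewer of 13 items (<25%) are missing", the ADAS-Cog total is scaled up; beyond that it is missing.
- "For ADCS-ADL, if 8 or fewer of 32 items (<25%) are missing", a similar algorithm applies; beyond 8 the total is missing.
- CDR-SB and MMSE are prorated "if only 1 box (of 6) of CDR is missing or if only 2 or fewer items (out of 11) are missing for MMSE"; beyond that they are missing.
- NPI-10 and FAQ are prorated if a single item of 10 is missing.

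The composites have their own rules. ADCOMS is missing if any component item is missing, and iADRS is missing if either component is missing.

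eCog is not named in Section 3.5, and nothing else in the supplied documents gives it a missing-item rule. The protocol's schedules (Section 5, Tables 1 to 4) specify the 39-item version. SAP Section 5.3.4 says "The by visit summary and MMRM analysis will be performed for MMSE, ISLT, eCog, ADCS-ADL, FAQ" and other endpoints.

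**The concern.** Every other multi-item questionnaire in the SAP 5.3.4 list has a stated tolerance for missing items. eCog, with 39 items, has none. Under the general sentence, a nearly blank form yields a total that counts in the by-visit summary and the MMRM exactly as a complete form does.

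Such a score is noisy. It is also biased if the answered items differ systematically in difficulty from the skipped ones.

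A sparse baseline form would do the most damage. Table 1 of the protocol schedules eCog only once before dosing, at Screening Visit 3. A poor baseline score would therefore enter every change score for that participant, as well as the baseline and baseline-by-visit terms of the model in SAP 5.3.2.1.

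**Working it through.** **1. The SAP's own limits as fractions** (items allowed missing divided by items in the scale, from SAP 3.5), and the same fraction applied to 39 items, rounded down:

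| Scale | Allowed missing | Fraction | Equivalent for 39 items |
|---|---|---|---|
| NPI-10, FAQ | 1 of 10 | 10.0% | 3 |
| CDR-SB | 1 of 6 | 16.7% | 6 |
| MMSE | 2 of 11 | 18.2% | 7 |
| ADAS-Cog 13 | 3 of 13 | 23.1% | 9 |
| ADCS-ADL | 8 of 32 | 25.0% | 9 |
| eCog | not stated | none | none |

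The ADAS-Cog 13 figure reproduces: 3/13 = 23.1%, which is below 25% as labelled.

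**2. What the general sentence does to eCog.** The SAP's prorating formula multiplies the observed total by the maximum total over the maximum for the completed items. The documents do not give the eCog item range. Assuming that all items share one range, the multiplier is 39/m for m answered items.

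- m = 1: 38/39 = 97.4% missing, multiplier 39.
- m = 30: 9/39 = 23.1% missing, multiplier 39/30 = 1.30.

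Nothing in the SAP sets the first of these to missing.

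**3. Imprecision of a prorated total.** Let s be the within-person SD of item scores, and treat the answered items as a random subset. The error SD of the prorated total around the full total is 39 × s × √[(1/m)(1 − m/39)].

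| Items answered (m) | Error SD |
|---|---|
| 1 | 38.5s |
| 5 | 16.3s |
| 10 | 10.6s |
| 30 | 3.4s |

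The ratio of one answer to 30 answers is 38.5/3.4, about 11, and does not depend on s.

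**4. Check on a relative scale.** Assume instead an exchangeable inter-item correlation ρ, which is not in the documents. The error SD relative to the SD of the full total is √[39²(1 − ρ)(1/m − 1/39)] / √[39(1 + 38ρ)].

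| ρ | m = 1 | m = 10 | m = 30 |
|---|---|---|---|
| 0.3 | 1.47 | 0.41 | 0.13 |
| 0.5 | 0.98 | 0.27 | 0.09 |
| 0.7 | 0.64 | 0.18 | 0.06 |

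A total from 30 answers carries little extra error. A total from one answer carries error of roughly the same order as the spread between participants.

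**5. The candidate limit.** 9/39 = 23.1% is below 25%; 10/39 = 25.6% is not. A limit of fewer than 25% therefore means at most 9 missing items, or at least 30 answered.

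**The case against.** The best reply is that the opening sentence merely introduces the scale-specific bullets. Read as unconditional, it conflicts with them. It would even prorate NPI-10 and FAQ with two or more items missing, since the SAP does not say what happens to those scales beyond one. On this reading eCog has no rule at all, and the one-item total is an inference rather than planned behaviour. This is a fair reading, but it does not remove the gap: eCog still has no limit, and the decision is left to programming.

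The placebo-controlled SAP may contain an eCog rule. It was not supplied, and this SAP defers to it on many topics, though not on missing items in Section 3.5. It matters here because eCog at baseline and Weeks 28, 56 and 78 falls in the placebo-controlled period. The first extension eCog visit is Week 108, after the Week 104 cut-off for the interim MMRM. Any fix must therefore agree with that document.

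Sparse forms may also be rare. Protocol Section 19.1.3 has caregiver-reported outcomes captured electronically, and Section 13.1 requires trained raters. Neither guarantees complete forms, but nothing in the documents shows that near-blank forms are expected.

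Three stronger readings are tempting and not supported:

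- **All efficacy totals are prorated without limit.** Six scales have explicit conditions, and ADCOMS and iADRS are not prorated from incomplete components.
- **The eCog analysis will carry an error of a known number of points.** The item SD, item range and scoring metric are not given, so only the ratios in the working can be stated. Even those describe single scores, not the treatment difference.
- **The ADCS-ADL limit is contradictory and should become 7.** Exactly 8 of 32 is 25.0%, so the <25% label is wrong at the boundary. But the count of 8 is stated twice, once for imputing and once for setting to missing, so the operative rule is clear. Only the label is off.

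**Conclusion.** The point holds for eCog alone. SAP 3.5 states a prorating rule that covers exploratory efficacy endpoints, limits it for six scales, and leaves the 39-item eCog without a limit. Read literally, any eCog form with at least one answer produces a total.

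The consequence is minor. The roughly 11-fold difference in error SD compares the extreme case of one answer with 30 answers, and assumes that answered items are a random subset. The frequency of sparse forms is unknown, so no effect on an eCog treatment estimate can be given. eCog is exploratory. CDR-SB, the primary efficacy endpoint, has its own limit of one missing box of six and is unaffected.

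**What to change.** Add one sentence to SAP 3.5: the eCog total is prorated only if fewer than 25% of items are missing (at most 9 of 39); otherwise the eCog score at that visit is missing. Check the placebo-controlled SAP first and keep the two documents consistent.

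The limit of 9 is a choice. The SAP's own fractions scale to between 3 and 9 items. Nine is suggested because 9/39 is exactly the ADAS-Cog 13 fraction of 3/13, and the added error at that limit is small.

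The cost is one sentence and the loss of a few sparse records, which the MMRM would then handle under its stated missing-at-random assumption. A sparse baseline form costs more: with only one scheduled pre-dose eCog, that participant would usually have no eCog change score.

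For ADCS-ADL, leave the count at 8. At most, correct the label to ≤25%.
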